**9.5.4.4. Subgroup Analysis Subsets**

The mean IOP comparison between the control and each of the two implant groups will be evaluated for the subsets based on the categories of each covariate described in Section 9.5.3). These subgroups will be re-examined and may be re-categorized or eliminated due to small sample size [REDACTED]

**9.5.5. Baseline Definition**

Unless specified otherwise, the baseline value for each variable is the value recorded at the last visit on or before treatment. For IOP measurement, the baseline is the measurement taken at Visit 2.

**9.6. Data Analyses**

**9.6.1. General Principles of Data Analyses**

The primary analysis for this Phase II study will be performed and summarized after all randomized subjects have had an opportunity to complete their 12-week visit.

The analyses of the safety outcomes will be based on the safety population defined in Section 9.5.4.2. The primary analyses of the efficacy endpoint (IOP) will be based on the ITT population defined in Section 9.5.4.1. The PP population (Section 9.5.4.3) will be used for the sensitivity analyses for the IOP.

Continuous variables will be summarized with means, standard deviations, medians, minimums, maximums, and number of non-missing observations for each treatment group. Other selected percentiles, such as the 25th percentile and 75th percentile may be presented for parameters that are not normally distributed or are suspected of

**CLINICAL PROTOCOL**

Date: September 16, 2016	Phase: Phase II Study	Protocol No.: GC-009
-----------------------------	--------------------------	-------------------------

exhibiting that tendency. Categorical variables will be summarized by counts and by percentage of subjects in corresponding categories.

**9.6.2. Subject Enrollment and Disposition**

The reasons for subject enrolled but not randomized (including screen failures) will be provided. Subject disposition will be summarized for all the randomized subjects. The summary including the number and percentage (based on total number of subjects randomized) of subjects in each of the following categories will be prepared for each of the three treatment groups.

- [REDACTED]
- [REDACTED]
- [REDACTED]
- [REDACTED]

Protocol deviations will also be summarized by the type of deviations and treatment groups.

**9.6.3. Subject Demographic and Baseline Characteristics**

The following parameters will be summarized by the standard methods for continuous and categorical variables described in Section 9.6.1.

The demographics include the following parameters:

- Age at informed consent
- Sex
- Race/Ethnicity
- Study eye

The baseline characteristics include the following:

- Type of disease (OAG or OHT)
- [REDACTED]
- Screening IOP
- Baseline IOP
- Baseline best spectacle corrected visual acuity (ETDRS)
- Baseline specular microscopy

**CLINICAL PROTOCOL**

Date: September 16, 2016	Phase: Phase II Study	Protocol No.: GC-009
-----------------------------	--------------------------	-------------------------

- Gonioscopy at screening
- Dilated fundus finding at screening
- Nerve abnormality at screening
- Vertical cup-to-disc ratio at screening
- Visual field at screening
- Pachymetry at screening
- Conjunctival hyperemia assessment at baseline
- Periorbital assessment at baseline
- Iris assessment at baseline
- Eyelash assessment (density, length) at baseline
- [REDACTED]

#### 9.6.4. Efficacy Analyses

##### 9.6.4.1. Primary Efficacy Analysis

The primary analyses of the mean IOP comparison between the control group and each of the two implanted groups at each time point from 1 week to 12 weeks will be based on [REDACTED]

[REDACTED] For each of the two implant groups, the least-squares mean of the treatment difference (Implant - Control) at each time point and the corresponding 95% confidence interval will be derived.

##### 9.6.4.2. Sensitivity Analysis

[REDACTED].

[REDACTED]

[REDACTED]

**CLINICAL PROTOCOL**

Date: September 16, 2016	Phase: Phase II Study	Protocol No.: GC-009
-----------------------------	--------------------------	-------------------------

**9.6.4.3. Analysis of Covariates**

[REDACTED]

**9.6.4.4. Subgroup Analysis**

For each sub-group described in Section 9.5.4.4, the repeated measurement model will be performed within each sub-group [REDACTED]

[REDACTED]

**9.6.4.5. Exploratory Analyses**

[REDACTED]

[REDACTED]

**9.6.5. Safety Analyses**  
No formal statistical testing will be conducted for the safety analyses. No imputation will be performed for the missing values. All summaries will be based on the available data of the safety population. The descriptive statistics described in Section 9.6.1 will be performed at each visit for the 3 treatment groups separately. Sections below described specific data handling for study drug exposure, surgical complications, adverse events, and best spectacle corrected visual acuity (BCVA).

**9.6.5.1. Study Drug Exposure**

Post-treatment systemic exposure to travoprost free acid will be evaluated by analyzing data from systemic drug concentrations in human plasma at Week 1-2, Week 12 and Month 12. The descriptive statistics for continuous variables will be

**CLINICAL PROTOCOL**

Date: September 16, 2016	Phase: Phase II Study	Protocol No.: GC-009
-----------------------------	--------------------------	-------------------------

used to summarize the concentration levels and the change from the pre-dose levels at each visit.

**9.6.5.2. Surgical Complications**

It is expected that more surgical complications will be reported for the implant groups than the control group. [REDACTED]

[REDACTED]

**9.6.5.3. Adverse Events**

All adverse event (AE) summaries will be restricted to Treatment Emergent Adverse Events (TEAE), which are defined as those AEs that occurred after the initial treatment at Visit 3. [REDACTED]

[REDACTED]. It should be noted that AEs that occurred after during the baseline washout will be summarized separated. The adverse event listings will be displayed by treatment group. The number of subjects experiencing a particular event, the percentage of subjects experiencing the event, and the total number of events will be presented. The following summaries will be created:

- TEAE by SOC and preferred term
- TEAE by SOC, preferred term and maximum severity. At each level of subject summarization, a subject is classified according to the highest severity if the subject reported one or more events. AEs with missing severity will be considered severe for this summary.
- TEAE by SOC, preferred term and closest relationship to study treatment (Related/Not Related). [REDACTED]
- Serious TEAEs by SOC and preferred term.

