## 1. Introduction

This Phase 2 study evaluates the safety and efficacy of two intraocular implants that elute travoprost at different rates in subjects with open-angle glaucoma (OAG) or ocular hypertension (OHT). The study duration is 36 months postoperative. One database lock will occur after all subjects have either completed the Month 36 visit or discontinued prematurely.

An analysis will be conducted after all subjects either completed the Month 3 visit or have discontinued prematurely prior to Month 3. At that time, the randomization code will be unmasked to the project team after all the data queries related to the efficacy and safety outcomes are resolved and corresponding data revisions are completed in the database.

This statistical analysis plan provides details of the planned analyses to be performed at the time of the Month 36 database lock. Shells of tables, listings and figures are presented in a separate document.

[figure not shown]
This document is based on Protocol Amendment 2 (16 September 2016). The statistical definitions and analytical methods described in this SAP supersede that in the protocol. Any revisions to the primary endpoint analyses and significant revisions to the secondary endpoint analyses will be made prior to the database lock. Reasons for such revisions will be described in the final Clinical Study Report (CSR).

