### 7.1.2. Adverse Events

All adverse event (AE) summaries will be restricted to Treatment Emergent Adverse Events (TEAE), which are defined as those AEs that occurred on/after the initial treatment at Visit 3. Verbatim terms reported by the study sites will be mapped to system organ classes (SOC) and preferred terms assigned using MedDRA (Medical Dictionary for Regulatory Activities) [REDACTED] for summary purposes. The adverse event listings will be displayed by treatment group. The number and of percentage subjects experiencing a particular event will be presented.

For a given AE and subject, if more than 1 severity grade is reported, the highest severity grade will be used for analysis.

If a subject experienced more than 1 relationship within an AE, the subject is counted once under maximum relationship. AEs with a missing relationship will be considered related for this summary; events classified as ‘possibly’, ‘probably’ or ‘definitely’ from eCRF will be considered ‘related’.

Adverse events will be classified into ocular AEs and non-ocular/non-study eye AEs. An ocular AE will be determined as indicated on the AE form of eCRF for the study eye only; a non-ocular/non-study eye AEs will include AEs with primary SOCs of eyes for non-study eye and AEs with primary SOCs not for eye.

All TEAEs, ocular TEAEs and non-ocular/non-study eye TEAEs will be summarized by treatment group separately in the following tables:

- Summary of adverse events
- TEAE by SOC and preferred term
- TEAE by SOC, preferred term and maximum severity.
- TEAE by SOC, preferred term and relationship (Related/Not Related) to study treatment.
- Serious TEAEs by SOC and preferred term.
- Ocular TEAEs by preferred term.

The TEAE listings will be prepared, sorted chronologically within subjects for the following types of AEs. Each listing will be displayed by treatment group.

- All AEs
- Serious AEs
- TEAEs leading to death
- TEAEs leading to withdrawal [REDACTED]

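### The TEAE tables visible in SAP 7.1.2 have no split by onset period, so for terms that can occur both around surgery and later they cannot show when an implant-arm excess arose.

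*Protocol*

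**What the plan says.** The SAP states that "The statistical definitions and analytical methods described in this SAP supersede that in the protocol", so SAP 7.1.2 is the governing text. It restricts the summaries to TEAEs, "which are defined as those AEs that occurred on/after the initial treatment at Visit 3". Protocol 9.6.5.3 has "which are defined as those AEs that occurred after the initial treatment at Visit 3", so the SAP wording also takes in events on the day of surgery. Neither visible definition has an upper time limit. SAP 1 says that "The study duration is 36 months postoperative".

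The two documents differ on what is reported per term:

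- Protocol 9.6.5.3: "The number of subjects experiencing a particular event, the percentage of subjects experiencing the event, and the total number of events will be presented".
- SAP 7.1.2: "The number and of percentage subjects experiencing a particular event will be presented". The event count is not restated.

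The tables listed in SAP 7.1.2 are an overall summary, SOC and preferred term, maximum severity, relationship, serious events, and ocular events by preferred term. The only visible division is by site: "Adverse events will be classified into ocular AEs and non-ocular/non-study eye AEs". A subject with several severity grades or relationships for one event is placed in the highest. SAP 4 takes percentages, by default, from the relevant cohort of the analysis set, not from subjects still being followed. SAP 7.1.1 calculates duration of exposure, but no visible text uses it to form event rates.

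The arms differ in the procedure they receive (Protocol 4.1): intraocular implantation in two, a sham procedure in the third. On surgical complications, Protocol 9.6.5.2 says: "It is expected that more surgical complications will be reported for the implant groups than the control group".

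**The concern.** Protocol 1 describes drug delivery for up to 3 years, and Protocol 3 makes good tolerability one of the two clinical hypotheses. A central safety question is therefore whether harm continues or begins after recovery from surgery.

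Real surgery against a sham makes an early excess of some ocular events in the implant arms likely. Where a term can occur both early and late, a single cumulative percentage puts operative events in the same cell as events from the retained implant or prolonged drug release. The highest-category rules add to this: one severe or related event in the first days can fix a subject's category for that term for 36 months.

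Two misreadings become possible. A late excess could be put down to surgery, or an implant that is well tolerated after recovery could look poorly tolerated because of the first weeks.

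**Working it through.** **No figure to reproduce.** The visible text gives no adverse event rate. The rates below are assumptions, shown as a range.

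**Inputs from the documents**

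- About 150 subjects randomised 1:1:1 (Protocol 4.1): 150/3 = 50 per arm.
- Week 12 visit at 91 days and Month 36 visit at 1095 days (Protocol 4.1): 91/1095 = 8.3% of follow-up. The SAP calls the Week 12 visit Month 3.

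**Assumptions for one preferred term**

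- Early risk e in an implant arm: 0%, 20% or 40%.
- Late risk l in that arm: 4% without a late excess, 12% with one. Control late risk is 4%.
- Early and late events are independent, and nobody drops out.

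**Formula.** The percentage of subjects with the term at any time is 1 − (1 − e)(1 − l). The late excess therefore moves it by (1 − e) × (12% − 4%).

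| Early implant risk | Pooled %, late 4% | Pooled %, late 12% | Shift (points) | Subjects of 50 |
|---|---|---|---|---|
| 0% | 4.0 | 12.0 | 8.0 | 4.0 |
| 20% | 1 − 0.80×0.96 = 23.2 | 1 − 0.80×0.88 = 29.6 | 6.4 | 3.2 |
| 40% | 1 − 0.60×0.96 = 42.4 | 1 − 0.60×0.88 = 47.2 | 4.8 | 2.4 |

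**Against control.** With a control early risk of 5%, the control figure is 1 − 0.95×0.96 = 8.8%.

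- At 20% early implant risk, the between-arm difference with the late excess is 29.6 − 8.8 = 20.8 points, of which the late excess supplies 6.4/20.8 = 31%.
- At 40%, the difference is 47.2 − 8.8 = 38.4 points, and the late share is 4.8/38.4 = 12.5%.
- With no early risk in either arm, the whole difference (12% − 4% = 8 points) is late, and nothing is masked.

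**What the event count would add.** Assume at most one early and one late event per subject. At 40% early risk the expected counts are 50×(0.40 + 0.04) = 22 without the late excess and 50×(0.40 + 0.12) = 26 with it. The full difference of 4 is kept, against 2.4 in the subject count. The total still does not say when the events occurred.

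**The case against.** The case against giving this much weight is substantial.

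- **Safety by time exists elsewhere.** Visual acuity, slit-lamp, gonioscopy, ophthalmoscopy, visual field, cup-to-disc ratio, pachymetry, endothelial cell density and hyperemia are summarised by scheduled visit (SAP 7.1.3 to 7.1.11), and TEAE listings run chronologically within subject. This stands. However, examination summaries do not give the severity, relationship or seriousness of adverse events, and listings give no comparative rate.
- **The Month 3 analysis helps.** Subtracting its subject percentages from those at Month 36 would be wrong, but the two together can recover a late risk: (47.2 − 40)/60 = 12%, or (42.4 − 40)/60 = 4%. This stands in part. The ratio is the late risk among subjects without an early event, so it equals the overall late risk only under independence. It also needs adverse event tables at that cut, which the visible text does not specify, and some subjects will be past Month 3 by then.
- **Small arms limit the gain.** Even with a perfect split, 12% against 4% is 6/50 against 2/50 (Fisher p = 0.27). This stands. The split describes timing and does not create power; safety has no formal testing in any case (Protocol 9.6.5).
- **Surgical complications are a separate outcome.** They have their own entry among the safety measures and their own protocol section. No visible text says that they are counted in the TEAE tables, or how often they are expected. The sentence in Protocol 9.6.5.2 supports the direction of an early excess, not its size in those tables.
- **Redaction.** Text is hidden in Protocol 9.6.5.2 and 9.6.5.3 and in SAP 7.1.2. The table list in SAP 7.1.2 reads without a break, but handling by period elsewhere cannot be excluded.

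A reader might infer that early surgical events would swamp any late implant or drug effect. The documents do not support that. The tables are by preferred term, so a term that arises only late is undiluted, and the loss for other terms depends on early rates that are not given. Nor does every planned table give only a subject percentage, since the protocol also promises event counts.

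**Conclusion.** The point holds in a limited form. In the visible text of SAP 7.1.2, every TEAE table covers one period from Visit 3 onward and reports subjects only. For terms that can arise both perioperatively and late, these tables, including those by maximum severity and maximum relationship, cannot date an implant-arm excess.

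Under the assumed rates, an 8-point late excess keeps its full size with no early risk and shrinks to 6.4 points at 20% and 4.8 points at 40%. These sizes rest on assumed risks, independence and no dropout. The structural point rests only on the absence of a visible period split.

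This is a worthwhile, cheap improvement to a descriptive safety analysis, not a defect that invalidates it.

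**What to change.** In SAP 7.1.2, keep the overall tables and add ocular TEAE tables by preferred term, maximum severity, relationship and seriousness for two onset periods:

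1. Surgery to the Month 3 visit.
2. After the Month 3 visit to Month 36.

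Count a subject once per term within each period, and apply the highest-severity and highest-relationship rules within the period. Use as the late-period denominator the subjects still in follow-up when that period starts. Restore the total number of events in all these tables, as Protocol 9.6.5.3 provides. State a fallback boundary, such as the nominal 91 days, for subjects who stay in the study but miss the Month 3 visit.

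The cost is SAP wording and a second set of tables, programmed from onset dates that the AE form already collects (Protocol 10). No design change or new data are needed. The downside is more output and smaller counts per cell.

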**9.6.5.4. Best Spectacle Visual Acuity (BSCVA)**

The number of ETDRS letter reads correctly will be summarized descriptively at each visit using the statistics for the continuous variables described in Section 9.6.1 for each of the three treatment group. The change in the number of ETDRS letters from baseline to the follow-up visits will be calculated for each subject. The change in the

**CLINICAL PROTOCOL**

Date: September 16, 2016	Phase: Phase II Study	Protocol No.: GC-009
-----------------------------	--------------------------	-------------------------

number of ETDRS will be summarized using the statistics for the continuous variables.

Additionally, the number and percentage of subjects will be summarized for each of the three treatment groups based on the following VA categories:

**10. ADVERSE EVENTS**

Adverse events will be monitored throughout the course of the study, and reported on an adverse event (AE) form. Any significant change in a subject's condition from baseline, regardless of causality, is to be considered an adverse event, unless the change is determined to be a continuation of a pre-existing condition that is documented in the subject's medical history. However, a clinically significant increase in frequency or worsening in severity of a pre-existing condition may indicate an adverse event. In addition, a clinically significant laboratory finding may also indicate an adverse event. Lack of efficacy of the study treatment for the condition being investigated is not an adverse event. Subjects should be asked using a general, non-direct question if there has been any change in how they feel from the previous visit (e.g., "How have you felt since the last visit?"). Direct questioning and examination should then be performed as appropriate. If an adverse event occurs, then an AE form must be completed including a description of the event, seriousness, severity, onset and duration, action taken, outcome, and relationship to study medication. A separate AE Form must be completed for each adverse event. All items on the AE form must be completed.

If an adverse event is ongoing at the time of study exit, then the investigator should perform reasonable follow-up efforts as necessary (e.g., telephone contact, post-study office visit) to determine the outcome of the event.

## CLINICAL PROTOCOL

Date:	Phase:	Protocol No.:
September 16, 2016	Phase II Study	GC-009

## 10.1.

## Phase: Phase II Study

Protocol No.:  
GC-009

The image is a high-contrast, black-and-white graphic. It features a large, dark, irregular shape on the left side, composed of several thick, horizontal black lines of varying lengths. To the right of this shape, there is a large, solid black rectangular area that extends across the width of the frame. The overall appearance is abstract and geometric.

### 10.3. Serious Adverse Event

Serious adverse events are defined as any findings that suggest a significant hazard, contraindication, side effect, or precaution. Any adverse event is considered a serious adverse event if it results in any of the following outcomes:

## - Death

**CLINICAL PROTOCOL**

Date: September 16, 2016	Phase: Phase II Study	Protocol No.: GC-009
-----------------------------	--------------------------	-------------------------

- Life or sight threatening
- In-subject hospitalization or prolongation of an existing hospitalization
- A persistent or significant disability/incapacity
- A congenital anomaly/birth defect

Important medical events that may not result in death, be life-threatening, or require hospitalization may be considered a serious adverse drug experience when, based upon appropriate medical judgment, they may jeopardize the subject and may require medical or surgical intervention to prevent one of the outcomes listed above. A life-threatening event is any event that places the subject at immediate risk of death from the event as it occurred; it does not refer to an event that hypothetically might have caused death if it were more severe. A sight-threatening event is any event that places the subject at immediate risk of permanently losing vision in either eye as a direct result of the event.

Serious, alarming, and/or unusual adverse events must be reported to Glaukos within 24 hours of the investigator's knowledge of the event:

[REDACTED]

An AE Form and supplemental SAE Report Forms must be completed as much as possible for all serious adverse events and faxed to Glaukos within 24 hours of knowledge of the event. When new significant information (including the outcome of the event) is obtained, the investigator should inform Glaukos by telephone or facsimile as soon as possible. Depending on the nature and seriousness of the AE, Glaukos may request copies of the ophthalmic and medical record of the subject as well as results of laboratory tests. If the subject was hospitalized, a copy of the discharge summary must be forwarded to Glaukos as soon as possible.

#### 10.4. Unexpected Adverse Event

An adverse event is considered “unexpected” if it is not listed in the investigator brochure or is not listed at the specificity or severity that has been observed, or is not consistent with the risk information described in the general investigational plan or protocol. For example, under this definition, hepatic necrosis would be unexpected.

Unexpected adverse events must be reported to Glaukos within 24 hours of the investigator's knowledge of the event:

[REDACTED]

An AE Form and supplemental SAE Report Forms must be completed as much as possible for all unexpected adverse events and faxed to Glaukos within 24 hours of knowledge of the event. When new significant information (including the outcome of the event) is obtained, the investigator should inform Glaukos by telephone or facsimile as

